### **3.2 Exclusion Criteria (Main Cohort)**

Participants will be excluded from the study for the following:

- 1 Patients with severe COVID-19 infection defined by pulmonary infiltrates on Chest X-Ray or CT imaging plus one of the following: room air  $\text{SaO}_2 \leq 92\%$ , room air  $\text{PaO}_2 < 70 \text{ mm Hg}$ , or  $\text{PaO}_2\text{-PaCO}_2 \geq 35 \text{ mm Hg}$ .
- 2 Contraindication to r-IFN $\alpha$  based on prior hypersensitivity, autoimmune hepatitis, decompensated liver disease.
- 3 Patients who have active acute myeloid leukemia or acute lymphoid leukemia or are allogeneic hematopoietic stem transplant recipients. Acute leukemia in remission and chronic leukemias are not exclusion criteria.
- 4 Cardiac events:
  - a. Acute coronary syndrome, myocardial infarction, or ischemia within past 3 months,
  - b. New York Heart Association classification of III or IV congestive heart failure (**Appendix A**)
- 5 Unwilling or unable to follow protocol requirements.
- 6 Patients with known serious mood disorders.
- 7 Any additional condition, such as pre-existing inflammatory lung disease, which in the Investigator's opinion deems the participant an unsuitable candidate to receive the study drugs.
- 8 Concurrent infections, e.g. bacterial pneumonia or sepsis, that would make it difficult to evaluate clinical response to therapy or study drug toxicities.
- 9 Therapies known to cause cytokine release syndrome (CRS), e.g. engineered T cells, within 30 days.
- 10 Patients at high risk for tumor lysis syndrome.
- 11 Concurrent active pneumonitis predating COVID-19, such as from checkpoint inhibitor therapy, chemotherapy-associated toxicity, or radiation pneumonitis.
- 12 Autoimmune disease that requires systemic immunosuppression.
- 13 Protocol-defined baseline abnormalities in cell counts, renal, or hepatic function.
- 14 Any additional condition which in the Investigator's opinion deems the participant an unsuitable candidate to receive the study drugs.

Refer to **Appendix E** for the Investigator Study Eligibility Verification Form (Main Cohort): Exclusion Criteria.

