### **3 INCLUSION AND EXCLUSION CRITERIA**

#### **3.1 Inclusion Criteria (Main Cohort)**

To be included in this study, participants must meet the following criteria:

- 1 Patients with cancer, with the exception of patients with active acute leukemia and allogeneic hematopoietic stem cell transplant recipients. Patients may be on active therapy or received therapy (e.g., chemotherapy, radiation, or surgery) within 7 years. Patients with active cancer who have not yet been treated (e.g. newly diagnosed cancer or early stage MDS or CLL) are eligible. Basal cell cancer and carcinoma in situ treated with local excision alone do not qualify for inclusion.
- 2 Presence of symptomatic infection, defined by fever ( $T \geq 38.0^{\circ}\text{C}$ ) OR respiratory symptoms (cough, nasal congestion, or shortness of breath), OR lung infiltrates on chest X-ray or CT imaging, Diagnosis of COVID-19 is based on PCR testing of respiratory samples.
- 3 Age equal to  $\geq 18$  years or older (children are excluded because COVID-19 typically has a milder course in children, and lack of safety data of this regimen in children).
- 4 Laboratory evaluation:
  - Platelet  $\geq 75,000/\mu\text{L}$
  - Hemoglobin  $\geq 9 \text{ g/dL}$
  - Hematocrit  $\geq 27\%$
  - Absolute Neutrophil Count (ANC)  $\geq 1000/\mu\text{L}$
  - Creatinine clearance  $\geq 50 \text{ mL/min}$  (Cockcroft-Gault Equation—note: plasma creatine instead of serum is used at Roswell Park)
  - Total bilirubin  $\leq 2 \times$  institutional ULN
  - AST (plasma) and ALT(plasma)  $\leq 2 \times$  institutional ULN
  - Plasma amylase and lipase  $\leq 2 \times$  institutional ULN
- 5 In the absence of COVID-19, a life expectancy of 6 months is expected.
- 6 Participant must understand the investigational nature of this study and sign an Independent Ethics Committee/Institutional Review Board approved written informed consent form prior to receiving any study related procedure.

**NOTE:** For blood chemistry labs, Roswell Park clinical blood chemistries are performed on plasma unless otherwise indicated.

Roswell Park Protocol No.: I-659920

Refer to **Appendix D** for the Investigator Study Eligibility Verification Form (Main Cohort): Inclusion Criteria.

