### **3.3 Inclusion Criteria (Expansion Cohort: Rintatolimod Plus Best Available Standard Care)**

We have added an expansion cohort to receive rintatolimod plus best available standard care. Because rIFN- $\alpha$  is not included in this group, eligibility criteria have been liberalized to include patients with more severe COVID-19, including those with respiratory failure, and exclusion criteria specific to rIFN- $\alpha$  have been removed. For patients who are eligible for both the main cohort and expansion cohort, enrollment in the Main Cohort will be prioritized because of the rationale that it might be more effective. To be included in the Expansion Cohort, cancer participants must meet the following criteria:

- 1 Patients with cancer or allogeneic stem cell transplant recipients with and without a cancer diagnosis.
  - Patients with cancer may be on active therapy or received therapy (e.g., chemotherapy, radiation, or surgery) within 7 years.
  - Patients with active cancer who have not yet been treated (e.g. newly diagnosed cancer or early stage MDS or CLL) are eligible.
  - Basal cell cancer and carcinoma in situ treated with local excision alone do not qualify for inclusion.
- 2 Presence of symptomatic infection, defined by fever ( $T \geq 38.0^{\circ}\text{C}$ ) OR respiratory symptoms (cough, nasal congestion, or shortness of breath) OR lung infiltrates by chest X-ray or CT imaging. Diagnosis of COVID-19 is based on PCR testing of respiratory samples. Severe infection is excluded (see Exclusion Criteria).
- 3 Age equal to  $\geq 18$  years or older (children are excluded because COVID-19 typically has a milder course in children, and lack of safety data of this regimen in children). In the absence of COVID-19, a life expectancy of 6 months is expected.
- 4 Participant or health care proxy must understand the investigational nature of this study and sign an Independent Ethics Committee/Institutional Review Board approved written informed consent form prior to receiving any study related procedure. There may be specific instances when the patient can't provide informed consent, e.g. they require mechanical ventilation and are sedated, in which case a health care proxy will be able to provide informed consent. Patients with temporary cognitive impairment will be consented once their capacity has returned. Patients with chronic cognitive impairment, e.g. dementia, that precludes informed consent will not be enrolled.

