### **3.4 Exclusion Criteria (Expansion Cohort)**

Participants will be excluded from the study for the following:

- 1 Patients with respiratory failure requiring mechanical ventilation with FIO2 of  $> 60\%$ .

Roswell Park Protocol No.: I-659920

- 2 Allogeneic hematopoietic stem cell transplant recipients with active pulmonary GvHD (any grade).
- 3 Cardiac events:
  - a. Acute coronary syndrome, myocardial infarction, or ischemia within past 3 months,
  - b. New York Heart Association classification of III or IV congestive heart failure (**Appendix A**)
- 4 Unwilling or unable to follow protocol requirements.
- 5 Any additional condition which in the Investigator's opinion deems the participant an unsuitable candidate to receive the study drugs.

Refer to **Appendix E** for the Investigator Study Eligibility Verification Form (Expansion Cohort): Exclusion Criteria.

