### **10.4 Duration of Study Treatment**

A total of 2 daily doses over a 4-day day period of treatment is planned.

The participant may stop treatment earlier than planned in the event that the following occurs:

- Unacceptable toxicity
- Progression to severe COVID-19 infection, defined by new or worse pulmonary infiltrates on Chest X-Ray or CT imaging plus one of the following: room air  $\text{SaO}_2 \leq 92\%$ , room air  $\text{PO}_2 < 70 \text{ mm Hg}$ , or  $\text{PAO}_2-\text{PaO}_2 \geq 35 \text{ mm Hg}$ , and/or requiring mechanical ventilation
- Withdrawal of consent from study
- Participant non-compliance with study requirements

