### **11.1 Screening**

Within 3 days prior to treatment initiation and may be the same day as initiation of study treatment:

- Recording of concomitant medications
- Medical and Surgical History
- Physical exam (lung auscultation), Vital Signs and weight;  $\text{SaO}_2$
- ECOG Performance Status Assessment
- Hematology
- Chemistry
- Arterial blood gas

Roswell Park Protocol No.: I-659920

- Serum HCG pregnancy testing (within 3 days of Day 1 in women of child-bearing potential only)
- EKG
- Chest X-ray or CT imaging (NOTE: If a chest CT is ordered as standard of care prior to starting treatment, a chest x-ray is not required)
- Nasopharyngeal swab
- Evaluations Performed on each day of treatment [(Day 1 and Day 3 (+ 1 day)]: Recording of concomitant medications
- Recording of Adverse Events
- Targeted physical exam
  - Auscultation of lungs
  - Vital Signs (temperature, blood pressure, pulse rate and respiratory rate, SaO2) will be performed pre- treatment and at 30 and 60 minutes post rintatolimod ( $\pm$  5 minutes)
- ECOG Performance Status Assessment
- Hematology
- Chemistry
- Blood (30cc) for correlative studies: On Day 1 treatment and Day 3 treatment, prior to treatment and within 1 hour after end of infusion treatment (two draws on each of these days).
- Nasopharyngeal swabs for viral quantification by quantitative PCR

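### Main Cohort exclusion 1 prints a third severity limb (PaO2 minus PaCO2) that conflicts with section 10.4 and the Appendix E form and, read literally, excludes patients with infiltrates because they are well oxygenated; separately, section 3.3 excludes severe infection without defining it.

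*Combined protocol and SAP*

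**What the plan says.** **Main Cohort.** Exclusion 1 of section 3.2 reads "Patients with severe COVID-19 infection defined by pulmonary infiltrates on Chest X-Ray or CT imaging plus one of the following: room air", followed by three alternatives: SaO2 of 92% or less, room-air PaO2 below 70 mm Hg, or a gas difference of at least 35 mm Hg. Any one of them, together with infiltrates, excludes. The gas difference appears in three places:

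- Section 3.2: "PaO}_2\text{-PaCO}_2 \geq 35" (extracted notation for PaO2 minus PaCO2).
- Appendix E, Main Cohort exclusion form, item 1: PaO2 minus PaO2, as extracted.
- Section 10.4: PAO2 minus PaO2. This list is introduced by "The participant may stop treatment earlier than planned in the event that the following occurs", so it governs stopping, not entry.

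The SaO2 and PaO2 thresholds are the same in all three places (10.4 writes PO2 for the second). Inclusion 2 of section 3.1 names infiltrates as one qualifying route: "OR lung infiltrates on chest X-ray or CT imaging". Section 11.1 lists "Arterial blood gas" among the screening tests, so the gas limb can be evaluated.

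**Expansion Cohort.** The opening of section 3.3 states "eligibility criteria have been liberalized to include patients with more severe COVID-19, including those with respiratory failure". Item 2 of the same section, repeated on the Appendix D form, states "Severe infection is excluded (see Exclusion Criteria"). The only respiratory threshold in section 3.4 is item 1, which begins "Patients with respiratory failure requiring mechanical ventilation with FIO" and sets the limit at an FIO2 above 60%.

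**The concern.** Entry to the Main Cohort depends on which page is read. The limbs are alternatives, so a misprinted third limb excludes patients by itself, however well the other two work. In 3.2 it also runs against the PaO2 limb beside it: one excludes low arterial oxygen, while the other, at a given PaCO2, excludes high arterial oxygen.

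Two things are at stake. First, patients with infiltrates whom inclusion 2 admits may be turned away, or a signed form may disagree with the protocol text and create an eligibility deviation. Second, sections 3.3 and 7 give the Main Cohort priority for patients eligible for both cohorts, so this criterion also decides cohort placement. With 10 patients planned for Phase IIa (section 19.1), a few misplaced patients change the make-up of the group.

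In the Expansion Cohort, item 2 points to exclusion criteria that never use or define the term it relies on, in a section whose opening says that sicker patients are to be admitted.

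**Working it through.** The plan states no figure to reproduce. The check applies each printed rule literally.

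**1. Eligibility window under 3.2, infiltrates present and SaO2 above 92%.** The patient must escape both remaining limbs:

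- not PaO2 < 70, so PaO2 ≥ 70;
- not PaO2 − PaCO2 ≥ 35, so PaO2 < 35 + PaCO2.

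The window is 70 ≤ PaO2 < 35 + PaCO2, with width PaCO2 − 35. The documents give no PaCO2 values, so these are assumed (mm Hg):

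| PaCO2 | 35 + PaCO2 | Eligible PaO2 |
|---|---|---|
| 30 | 65 | none |
| 35 | 70 | none |
| 40 | 75 | 70 to below 75 |
| 45 | 80 | 70 to below 80 |
| 50 | 85 | 70 to below 85 |

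**2. Appendix E as extracted.** PaO2 − PaO2 = 0, and 0 ≥ 35 is never true. The form reduces to infiltrates plus SaO2 ≤ 92% or PaO2 < 70.

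**3. Section 10.4.** The documents do not define PAO2. It is taken here as alveolar oxygen, with assumed room air 0.21, water vapour 47, respiratory quotient 0.8, and barometric pressure (Pb) 760 or 740:

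PAO2 = 0.21 × (Pb − 47) − PaCO2/0.8

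- PaCO2 40: 149.73 − 50 = 99.73 at 760; 145.53 − 50 = 95.53 at 740.
- PaCO2 30: 149.73 − 37.5 = 112.23 at 760; 145.53 − 37.5 = 108.03 at 740.

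**4. The same patients under each text** (infiltrates present, SaO2 taken as above 92%):

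| PaO2/PaCO2 | 3.2 difference | 3.2, all limbs | Appendix E as extracted, all limbs | 10.4 difference (Pb 760; 740) |
|---|---|---|---|---|
| 95/40 | 55, met | severe | not severe | 4.7; 0.5, not met |
| 80/40 | 40, met | severe | not severe | 19.7; 15.5, not met |
| 72/40 | 32, not met | not severe | not severe | 27.7; 23.5, not met |
| 75/30 | 45, met | severe | not severe | 37.2, met; 33.0, not met |
| 60/40 | 20, not met | severe (PaO2 < 70) | severe (PaO2 < 70) | 39.7; 35.5, met |

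If the form in fact carries the 10.4 expression, the 95/40 patient still passes the form and still fails 3.2. The conflict between 3.2 and the form therefore does not depend on how Appendix E was read from the PDF.

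**5. Expansion Cohort.** No arithmetic applies. The opening of 3.3 admits respiratory failure, and item 4 provides proxy consent for sedated, ventilated patients. Item 2 excludes severe infection and refers onward. Section 3.4 bars ventilation with FIO2 above 60% and does not use the term. If item 2 means that criterion, the texts fit together. If it takes the 3.2 definition, it contradicts its own opening.

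**The case against.** The strongest reply is that this is a typographical slip with limited reach. Much of that stands:

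- **The criteria as a whole.** A reader might infer that the severity criteria are unusable in both cohorts. They are not. The SaO2 and PaO2 limbs agree wherever they appear and still work, the gas fault bites only when infiltrates are present, and the Expansion criteria contain no gas-difference limb.
- **Appendix E.** The extracted form differs from 10.4 only in the case of one letter, so it may be a PDF-reading error. The source page should be checked before anyone says that the form's limb can never be met. PaCO2 in 3.2 is a different quantity and is less likely to be such an error.
- **Safety.** A reader might infer that the form weakens a safety gate. Even as extracted, it excludes patients with infiltrates and SaO2 ≤ 92% or PaO2 < 70, and items 7 and 14 let the investigator exclude unsuitable patients.
- **Accrual.** A reader might link this to the accrual difficulty reported in section 9. That text attributes the difficulty to interferon contraindications, and nothing shows that anyone was excluded on the gas limb.
- **Endpoints.** The clinical complications are secondary, and section 8.2 says that the study is not powered for them.
- **Expansion Cohort.** Reading item 2 as pointing to item 1 of 3.4 largely removes the conflict.

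The reply does not rescue 3.2 itself. Because the limbs are alternatives, two sound limbs do not offset one that excludes on its own.

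**Conclusion.** The concern holds in a limited form. As printed, exclusion 1 of 3.2 is an operative entry rule that, for patients with infiltrates, leaves a PaO2 window of 5 mm Hg at PaCO2 40, 10 mm Hg at 45, and none at 35 or below. It contradicts the Main Cohort form, and it uses a different expression from the stopping condition in 10.4. The window rests on literal reading, on SaO2 above 92%, and on the assumed PaCO2 values. The comparison with 10.4 also rests on the alveolar assumptions stated above. How many patients are affected cannot be estimated, because the documents do not give the proportion with infiltrates or their blood gases.

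The Expansion Cohort wording is a separate and lesser point: an undefined term with a workable reading that the text does not state. This should be corrected as an inconsistency between texts. No view is taken here on which clinical expression or threshold is right.

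**What to change.** 1. Check the source page of the Appendix E Main Cohort form to establish what it prints.
2. Reconcile section 3.2, section 10.4 and Appendix E to one identical gas expression, chosen and confirmed by the clinical lead, with its symbols defined once.
3. Reconcile item 2 of section 3.3 and its copy in Appendix D with the opening of 3.3 and with section 3.4, either by deleting the sentence or by naming the 3.4 criterion to which it refers.
4. If patients have already been screened, check whether any with infiltrates were classified differently by 3.2 and by the form.

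The cost is an amendment to protocol and form wording, with no added procedures or visits; step 4 needs only existing screening records.

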### **3.3 Inclusion Criteria (Expansion Cohort: Rintatolimod Plus Best Available Standard Care)**

We have added an expansion cohort to receive rintatolimod plus best available standard care. Because rIFN- $\alpha$  is not included in this group, eligibility criteria have been liberalized to include patients with more severe COVID-19, including those with respiratory failure, and exclusion criteria specific to rIFN- $\alpha$  have been removed. For patients who are eligible for both the main cohort and expansion cohort, enrollment in the Main Cohort will be prioritized because of the rationale that it might be more effective. To be included in the Expansion Cohort, cancer participants must meet the following criteria:

- 1 Patients with cancer or allogeneic stem cell transplant recipients with and without a cancer diagnosis.
  - Patients with cancer may be on active therapy or received therapy (e.g., chemotherapy, radiation, or surgery) within 7 years.
  - Patients with active cancer who have not yet been treated (e.g. newly diagnosed cancer or early stage MDS or CLL) are eligible.
  - Basal cell cancer and carcinoma in situ treated with local excision alone do not qualify for inclusion.
- 2 Presence of symptomatic infection, defined by fever ( $T \geq 38.0^{\circ}\text{C}$ ) OR respiratory symptoms (cough, nasal congestion, or shortness of breath) OR lung infiltrates by chest X-ray or CT imaging. Diagnosis of COVID-19 is based on PCR testing of respiratory samples. Severe infection is excluded (see Exclusion Criteria).
- 3 Age equal to  $\geq 18$  years or older (children are excluded because COVID-19 typically has a milder course in children, and lack of safety data of this regimen in children). In the absence of COVID-19, a life expectancy of 6 months is expected.
- 4 Participant or health care proxy must understand the investigational nature of this study and sign an Independent Ethics Committee/Institutional Review Board approved written informed consent form prior to receiving any study related procedure. There may be specific instances when the patient can't provide informed consent, e.g. they require mechanical ventilation and are sedated, in which case a health care proxy will be able to provide informed consent. Patients with temporary cognitive impairment will be consented once their capacity has returned. Patients with chronic cognitive impairment, e.g. dementia, that precludes informed consent will not be enrolled.

**NOTE:** For blood chemistry labs, Roswell Park clinical blood chemistries are performed on plasma unless otherwise indicated.

Refer to **Appendix D** for the Investigator Study Eligibility Verification Form (Expansion Cohort): Inclusion Criteria.

### **3.4 Exclusion Criteria (Expansion Cohort)**

Participants will be excluded from the study for the following:

- 1 Patients with respiratory failure requiring mechanical ventilation with FIO2 of  $> 60\%$ .

Roswell Park Protocol No.: I-659920

- 2 Allogeneic hematopoietic stem cell transplant recipients with active pulmonary GvHD (any grade).
- 3 Cardiac events:
  - a. Acute coronary syndrome, myocardial infarction, or ischemia within past 3 months,
  - b. New York Heart Association classification of III or IV congestive heart failure (**Appendix A**)
- 4 Unwilling or unable to follow protocol requirements.
- 5 Any additional condition which in the Investigator's opinion deems the participant an unsuitable candidate to receive the study drugs.

Refer to **Appendix E** for the Investigator Study Eligibility Verification Form (Expansion Cohort): Exclusion Criteria.

### **3.5 Inclusion of Women and Minorities**

Both men and women and members of all races and ethnic groups are eligible for this study.

### **3.6 Special Populations**

The following special populations will be excluded:

- Chronically cognitively impaired adults (e.g. those with dementia) with impaired decision-making capacity
- Individuals who are not yet adults (infants, children, teenagers)
- Pregnant women
- Prisoners

## **4 LOCAL AND STUDY-WIDE NUMBER OF SUBJECTS**

Maximum number of Roswell Park subjects: The anticipated number of subjects required for the main portion of the study is 44. All patients must have cancer and need not be established Roswell Park patients. The modification of the protocol triggered by the observed high effectiveness of the treatment in the first patient who received rintatolimod alone will include additional 20 cancer patients (Expansion Cohort).

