### **4.1 Target Accrual**

**Main Cohort:** Up to 44 patients are expected to be needed to estimate the biologic impact of this regimen and establish a preliminary estimate of efficacy. This number includes the following tiers of the dose-escalation of IFN $\alpha$  (3+3 design with 0, 5 MU/M $^2$ , 10 MU/M $^2$ , and 20 MU/M $^2$ ). Once an MTD is established, subsequent patients (n = 10) will receive rintatolimod + IFN $\alpha$  (at the MTD or, in the absence of an MTD, at 20 MU/M $^2$  IFN $\alpha$ ) as well as standard of care. Total accrual time is expected to take 36 months.

**Expansion Cohort:** In addition, we will accrue a maximum of 20 patients on Expansion Cohort, who will receive rintatolimod and best available standard care.

Roswell Park Protocol No.: I-659920

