## 7 STUDY TIMELINES

Main Cohort: A maximum of 44 evaluable participants will be enrolled to the study over up to 36-months. Patients will be followed until Day 30 after initiation of the study regimen.

Expansion Cohort: A maximum of 20 evaluable participants will be enrolled to the study over up to 36-months. Patients will be followed until Day 30 after initiation of the study regimen.

Enrollment in the Main Cohort and Expansion Cohort will be done concurrently. If a patient is eligible for enrollment in both the Main and Expansion Cohort and is willing to be enrolled in either cohort, priority will be given to the Main Cohort.

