## **19 STATISTICAL PLAN**

### **19.1 Study Design/Endpoints**

This is prospective Phase I/IIa trial basket trial of i.v. rintatolimod administered with or without i.v. IFN $\alpha$  (INTRON $\circledR$  A) in two cohorts of patients: Main Cohort and Expansion Cohort. Only Main Cohort subjects will participate in the Phase I 3+3 portion of this study. The Expansion

Roswell Park Protocol No.: I-659920

Cohort will consist of rintatolimod without IFN $\alpha$ . Neither cohort is randomized. The kinetics of nasopharyngeal viral load will be assessed based on baseline values and on treatment and EOT values. In the Expansion Cohort, the kinetics of nasopharyngeal viral load will be compared with historical controls consisting of Roswell Park patients with COVID-19 of varying severity. All patients will receive best available standard of care in addition to study drug regimens.

**Phase I.** The Phase I component of the protocol consists of a 3+3 design with four dose levels of IFN $\alpha$  (0, 5 MU/M, 10 MU/M and 20 MU/M ) and fixed dose rintatolimod (200 mg per day) administered on Days 1 and 3. The sample size for the Phase I trial may range from n=3 to 24.

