### **Primary Endpoint**

- The primary safety endpoint is the frequency of grade 3 or 4 AEs considered to be possibly, probably, or definitely related to the treatment regimen.

**Phase IIa.** The Phase IIa component of the trial is designed to be a single arm trial of IFN $\alpha$  (at MTD, if reached, otherwise at 20 MU/M) + rintatolimod along with the best available standard of care. Using each patient's baseline nasopharyngeal viral load, we will evaluate to what extent the study regimen reduces viral load relative historical institutional benchmarks. The sample size will be n=10.

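### The Main Cohort maximum of 44 is 10 above the sum of its stated parts: at most 24 in Phase I plus 10 in Phase IIa is 34

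*Combined protocol and SAP*

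**What the plan says.** Three sections give the Main Cohort size as 44. Section 4 says "The anticipated number of subjects required for the main portion of the study is 44". Section 4.1 says "Up to 44 patients are expected to be needed to estimate the biologic impact of this regimen and establish a preliminary estimate of efficacy"; it adds that the figure covers the escalation tiers, and then names 10 subsequent patients at the MTD or the top dose. Section 7 says "A maximum of 44 evaluable participants will be enrolled to the study over up to 36-months".

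Section 19.1 gives the components. For Phase I: "The Phase I component of the protocol consists of a 3+3 design with four dose levels of IFN" alpha, and "The sample size for the Phase I trial may range from n=3 to 24". Phase IIa is described there as a single-arm trial, with "The sample size will be n=10". Section 19.3 bases its power statement on the same 10 patients.

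The Expansion Cohort of up to 20 patients is described in Sections 4 and 4.1 as additional, and Section 7 gives it a separate maximum. Section 19.4 says the trial is not randomized.

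**The concern.** A stated maximum should be at least traceable to the parts that make it up. Here the parts are listed, each has its own ceiling, and they do not sum to the total. Describing 44 as a ceiling does not resolve this, because 34 is already the largest number the listed parts can produce, and Section 4 also presents 44 as the number required.

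The accrual maximum governs how many patients may be treated. Section 2.3 acknowledges that the regimen has not been evaluated in patients with a respiratory viral infection and might worsen inflammatory lung injury. As written, the protocol authorises 10 more exposures than its statistical plan accounts for and gives no reason for them.

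**Working it through.** **Inputs**

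- Dose levels in Phase I: 4 (Sections 4.1, 19.1 and 19.2.1).
- Patients per level: 3, with 3 more if one of the first three has a DLT, so at most 6 (Section 19.2.1).
- Phase IIa: 10 (Sections 4.1, 19.1 and 19.3).
- Expansion Cohort: 20, outside the Main Cohort (Sections 4, 4.1 and 7).
- Stated Main Cohort maximum: 44 (Sections 4, 4.1 and 7).

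**Step 1: reproduce the Phase I ceiling.** 4 levels × 6 patients = 24. This agrees with the upper limit in Section 19.1.

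**Step 2: sum the Main Cohort.** 24 + 10 = 34.

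**Step 3: compare with the stated figure.** 44 − 34 = 10 patients, and 44/34 = 1.29, so the stated maximum is 29% above the derivable one. Ten is the smallest possible gap. If all four levels are completed without a DLT, Phase I uses 4 × 3 = 12, the Main Cohort is 12 + 10 = 22, and the gap is 44 − 22 = 22.

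**Step 4: try the ordinary explanations for 44.**

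- *Dropout inflation.* Dividing 34 by (1 − d) gives 34/0.90 = 37.8, so 38, at d = 10%, and 34/0.80 = 42.5, so 43, at d = 20%. Reaching 44 needs d = 1 − 34/44 = 22.7%. No dropout rate is given anywhere.
- *Expansion Cohort counted inside the 44.* 24 + 20 = 44, but this leaves no room for Phase IIa. All three parts together make 24 + 10 + 20 = 54. Sections 4, 4.1 and 7 also place the 20 outside the 44.
- *A second Phase IIa arm of 10.* 24 + 10 + 10 = 44 exactly. The current Phase IIa has one arm and the trial is not randomized, so this does not describe the present design. Traces of a two-group design do remain: Section 9 mentions control arms, and the intention-to-treat definition in Section 19.1 refers to randomization.

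**Step 5: carry the difference to the whole study.** The stated maxima imply 44 + 20 = 64. The components give 34 + 20 = 54.

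**The case against.** The sum itself is hard to dispute, but several stronger readings a reader might draw from it are not supported.

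*That the extra 10 would have no dose and no analysis.* Table 1 and Section 10 assign a regimen to any patient enrolled after escalation, and Section 10 gives that portion a purpose in safety and viral load. Section 19.1 puts every consented, dosed patient in the safety analysis. What is missing is a planned count and a reason for it.

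*That Phase IIa would double to 20 after data are seen, undoing its alpha.* No section provides for this; Sections 4.1, 19.1 and 19.3 all fix 10. Enlarging a one-sample test does not in itself alter its 0.05 level. Only an enlargement that depends on the data would do so, and none is planned. The fair statement is that the 44 does not exclude it.

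*That the word evaluable rules out any margin for losses.* It appears with the 44 only in Section 7. A patient evaluable for efficacy under Section 19.1 could still lack a complete DLT window or some of the swabs needed for the AUC. The supportable claim is narrower: no allowance is stated.

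*That the protocol states a study total of 64.* It does not; 64 is the sum of two separately stated maxima.

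*That 44 is certainly a remnant of a two-arm design.* The exact match and the leftover wording make this plausible, but the documents do not say so. It remains possible that the sponsor intends the 10 and omitted the explanation.

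Finally, neither the powered test nor the escalation rules use 44. That limits the consequence but does not reconcile the numbers.

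**Conclusion.** Wrong as written. The Main Cohort maximum of 44 exceeds the sum of its stated components by 10 patients (44 against 34, or 29%). With the Expansion Cohort the implied total is 64 against 54.

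The conclusion rests on two readings that the documents support: that six patients per dose level is the 3+3 limit, which reproduces the protocol's own 24, and that Phase I and Phase IIa are the only Main Cohort components, since no other is described. Which figure is out of date cannot be proved from the text. The single-arm, non-randomized description makes 34 the likelier current number. The error lies in the accrual ceiling; it does not by itself invalidate the escalation or the Phase IIa test.

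**What to change.** Reconcile Sections 4, 4.1 and 7 with Section 19.1, in one of two ways.

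1. Restate the Main Cohort maximum as 34 (24 + 10) in all three sections. If a study total is given, it becomes 54. The cost is a wording amendment: authorised accrual falls by 10, and every planned analysis keeps its patients.
2. If the extra 10 are intended, state what they are for and how they will be analysed. Confirm that the Phase IIa primary test stays at n = 10, or restate its power in Section 19.3 for the new number. If they are an allowance for incomplete data, give the assumed rate and the replacement rule. This costs a short justification, plus a revised calculation if the size of the primary test changes.

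Under either option, the remaining references to control arms in Section 9 and to randomization in Section 19.1 should be brought into line with the current design, so that the basis of the total is clear.
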